Patients will be followed up in regular intervals after the initial attempt at rhythm control. The minimum follow up interval is every three months. More frequent follow up may be scheduled as deemed necessary by the treating physician.

[figure not shown]
At the time of the first attempt at rhythm control, at the 3 month follow up, and at the 6 month follow up all study patients will be assessed again for:

Weight, BMI, Hemoglobin A1c, serum CRP, eGFR, liver function tests (AST, ALT, ALP, bilirubin, albumin, INR), B12, lactic acid, number of antiarrhythmic agents, presence of AF by EKG, and Atrial Fibrillation Severity Score.

At each 3-month and 6-month follow up, data will be reviewed by a designee who will use the criteria described below for reporting to the Medical Monitor. The patient will also be assessed for the occurrence of any adverse events as defined below and adverse events will be reported to the medical monitor.

At the end of 6 months of therapy, the decision to continue Metformin beyond 6 months will be made in conjunction with the patient's treating cardiologist and primary care physician.

Figure 1.

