## **Selection and Withdrawal of Subjects:**

Inclusion criteria: All individuals diagnosed with Atrial Fibrillation and choosing to undergo a rhythm control strategy at Robert Packer Hospital with a BMI  $\geq$  27 will be eligible for the study. All subjects must be able to understand and willing to sign a written informed consent document.

Exclusion criteria: Individuals who are already taking metformin or other antidiabetic medications including insulin, have a diagnosis of diabetes, have a known allergy or FDA-labeled contraindication to taking metformin, eGFR below 30 mL/min per 1.73 m^2 or other clinical diagnosis of advanced renal disease,, have acute or chronic metabolic acidosis (serum bicarbonate <22 mEq/L), have a history of significant alcohol use (>2 drinks/day on average), have a history of hepatic dysfunction (serum bilirubin 1.5X greater than the upper limit of normal), have a history of New York Heart Association (NYHA) Class III or IV heart failure, or are pregnant will be excluded from the trial.

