#### **Assessment of Safety:**

A Medical Monitor will be utilized to provide general oversight and safety considerations for this study. The Medical Monitor will provide advice to the Sponsor-Investigator regarding actions the committee deems necessary for the continuing protection of subjects enrolled in this study. The Medical Monitor will be charged with assessing such actions in light of an acceptable risk/benefit profile for metformin. The Medical Monitor will act in an advisory capacity to the Sponsor-Investigator and will monitor subject safety data for the study.

All patients included in the study will have monitoring of renal function, hepatic function, and serum lactic acid at baseline, at the time of ablation or initiation of rhythm control, and at 3-month and 6-month follow ups. This data will be reviewed by an investigator who is not involved in the outcome analysis. This investigator will be a mid-level who will be assigned to check the routine labs. The parameters for immediate reporting to one of the study coordinators are the following- creatinine greater than or equal to 1.5 in males or 1.4 in females, elevated lactic acid, or serum bilirubin >1.5x the upper limit of normal. Exclusion criteria will also be reviewed at each follow up, and if at any point a patient meets the exclusion criteria for the study or has an unexpected adverse event they will be withdrawn from the study.

Routine reports will be provided to the Medical Monitor every 2 months and will include rates of disenrollment, reason for disenrollment, unexpected adverse events, and mortalities. If a statistically significant harm is detected in the analysis of the safety data collected at 2 month intervals the protocol will be terminated.

Adverse events will be solicited at routine follow-up with a designee and are defined as follows: .

Lactic Acidosis – lactic acid >2.1 mmol/L as measured at either routine follow up or if measured during a hospitalization for any reason

Thromboembolic event – any stroke, mesenteric ischemia, limb ischemia, or other event determined to be of an embolic etiology secondary to atrial fibrillation Vitamin B12 levels and any change from baseline at the 3 and 6 month timepoints will be measured and submitted.

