Adverse events will be reviewed every 2-months and a statistical analysis will be done. If the analysis finds that any of these adverse events have occurred more frequently in either group in a statistically significant manner, the trial will be stopped.

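### Lactic acidosis is defined by a lactate value alone, and a significant arm difference in it stops the trial, so raised lactate without acidosis would be reported as lactic acidosis and could end the study

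*Combined protocol and SAP*

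**What the plan says.** All references are to the combined protocol and SAP.

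- **Event definition (Assessment of Safety).** Lactic acidosis is "lactic acid >2.1 mmol/L as measured at either routine follow up or if measured during a hospitalization for any reason". No pH, bicarbonate, symptom or repeat measurement is required.
- **Stopping rule (end of Assessment of Safety).** "Adverse events will be reviewed every 2-months and a statistical analysis will be done". If it shows that "any of these adverse events have occurred more frequently in either group in a statistically significant manner, the trial will be stopped".
- **Second stop (same section).** "If a statistically significant harm is detected in the analysis of the safety data collected at 2 month intervals the protocol will be terminated".
- **Monitoring.** Lactate is measured in all patients at baseline, ablation, 3 months and 6 months, and elevated values are reported immediately. Under Trial Design, "adverse events will be reported to the medical monitor". The two-monthly report "will include rates of disenrollment, reason for disenrollment, unexpected adverse events, and mortalities"; lactate by arm is not named. The Medical Monitor is advisory.
- **An acidosis criterion exists elsewhere.** Selection and Withdrawal of Subjects excludes "acute or chronic metabolic acidosis (serum bicarbonate <22 mEq/L"), and Assessment of Safety adds: "Exclusion criteria will also be reviewed at each follow up". Bicarbonate is nevertheless missing from the listed follow-up laboratory tests, and the event definition does not use it.
- **Background risk (Potential Risks).** Lactic acidosis is put at about 0.03 per 1,000 patient-years (package insert) or 4.3 per 100,000 (pooled review).

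**The concern.** The event that will be counted is a single laboratory value, but it carries the name of the rare and serious condition described under Potential Risks. Two things follow. First, the safety results would list patients as having lactic acidosis when no acidosis was shown. Second, both stopping sentences are mandatory and neither passes through the Medical Monitor's judgement. A modest difference in lactate between arms, without acidosis, could therefore end an 800-patient trial before the six-month rhythm data are in.

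**Working it through.** **The plan's own figure.** The only design figure that can be recomputed is the sample size. For 30% v 21% (a 30% relative reduction), two-sided .05 and 80% power, the pooled-variance formula gives 367 per arm, and 389 with continuity correction. 389/0.97 = 401.03, rounded up to 402, against the stated 400. It reproduces and is not in dispute.

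**Expected cases at the quoted rates.** Each metformin patient is on study for 1.5 months before ablation and 6 months after.
- Patient-years: 400 × 7.5/12 = 250.
- Package insert: 250 × 0.03/1,000 = 0.0075 cases.
- Pooled review: 250 × 4.3/100,000 = 0.011 cases.

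**Patients carrying the label.** The documents give no rate of lactate above 2.1. Suppose 2.1 is the control 97.5th centile. With three independent on-study samples, 1 − 0.975³ = 0.073, and 400 × 0.073 = 29. With two samples (3 and 6 months) and within-patient correlation 0.5, the simulation gives 18. At the 99th centile the range is 7.5 to 12.

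**Chance of stopping.**
- From the protocol: 400 per arm, five years' accrual, two-monthly reviews, two-sided .05.
- Assumed: even accrual; a Pearson test at each review; normally distributed lactate; within-patient correlation 0 or 0.5; samples at 4.5 and 7.5 months after randomisation, with or without the ablation sample at 1.5; each patient counted at first exceedance; tests at months 2, 4, ..., 68; stop at the first p < .05 in either direction.
- Size: 6,000 simulated trials per setting (Monte Carlo standard error at most 0.65 points). Ranges span the sampling and correlation settings; a few upper bounds include an extra point seen on repeat runs.

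| Metformin shift in lactate | Ever stops, 2.1 = 97.5th centile | Stops by month 30, 97.5th | Ever stops, 2.1 = 99th centile |
|---|---|---|---|
| none | 23-27% | 16-19% | 18-21% |
| 0.1 SD | 30-39% | 19-25% | not tabulated |
| 0.2 SD | 52-69% | 29-41% | 36-50% |
| 0.3 SD | 77-93% | 45-65% | 58-76% |

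At month 30, 800 × 30/60 = 400 patients are enrolled and 800 × 22.5/60 = 300 have six-month data.

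**Separating definition from repeated testing (97.5th centile).** Relative to no shift, the shift itself adds 7-12 points at 0.1 SD, 29-42 at 0.2 SD and 54-67 at 0.3 SD. A single final test would give about 5% with no shift, 10-15% at 0.1 SD and 31-49% at 0.2 SD. So the no-shift figure and most of the 0.1 SD figure reflect the unadjusted looks. At 0.2 SD and above a substantial part comes from what is counted.

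**Sensitivity (97.5th centile).** With no test before 10 total events: 18-21%, 48-67% and 76-93% at no shift, 0.2 SD and 0.3 SD. With Fisher's exact test at each review: 16-17% at no shift and 74-90% at 0.3 SD.

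**After the fix.** Pearson's statistic for k v 0 at 400 per arm is (k/400)² / [p(1−p)·2/400], with p = k/800. For k = 3 it is 3.01 (p = 0.083); for k = 4 it is 4.02 (p = 0.045). With no drug effect, the false-stop probability is about 0%, 2%, 7% and 14% when 0.011, 1, 2 and 4 cases per arm are expected. With 4 expected on metformin and 0.011 on control, the trial stops in 56% of runs.

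**The case against.** **The premise is not in the documents.** A reader might infer that metformin raises lactate and that the trial will therefore stop. The documents do not support that. The only lactate statement, under Potential Risks, reports no evidence of an increase compared with other antihyperglycemic treatments. Users of such drugs are excluded here and the control arm gets no metformin, so the statement neither supports nor rebuts a shift against control. The 0.1, 0.2 and 0.3 SD shifts are illustrations.

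**The event may not be common.** Its frequency is assumed. At the 99th centile only 2-3% of controls would be labelled. Potential Risks also gives no diagnostic definition behind its rates, so they cannot be applied exactly to any redefined event.

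**The test is inferred.** The Statistics section assigns Pearson's test to outcomes; for safety the plan promises only an analysis. Fisher's test lowers the no-shift figures appreciably and the large-shift figures less.

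**Much of it is multiplicity.** This stands for no shift and for most of the 0.1 SD result. It does not stand at 0.2 SD and above, and adjusting alpha would leave the definition unchanged.

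**A sensitive trigger is a legitimate conservative choice in non-diabetic patients.** That stands as a view on risk tolerance. It does not justify the label.

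**Existing safeguards.** Immediate reporting, withdrawal of patients who meet exclusion criteria, and Medical Monitor oversight all exist. None softens the mandatory stop. The harm sentence need not be a separate trigger on lactate, and the point does not depend on it.

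**Conclusion.** The point holds. The definition lacks an acidosis criterion and the stop on it is mandatory; both are plain from the text. That raised lactate without acidosis would be reported as lactic acidosis follows directly. That it could end the trial follows too, but how likely this is rests on assumptions: Pearson tests at .05 every two months, normal lactate, and 2.1 as the control 97.5th centile. On those, the stop probability is about 52-69% at a 0.2 SD shift and 77-93% at 0.3 SD, or 36-50% and 58-76% if 2.1 is the 99th centile.

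The 23-27% with no shift should not be read as the cost of the definition. It is the cost of repeated unadjusted testing, a separate issue that this point does not repair. Nor should the table be read as a forecast, since the documents supply no shift. Confidence is high on the wording and moderate on the consequence.

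**What to change.** 1. Rename lactate above 2.1 mmol/L elevated lactate. Keep it a listed adverse event with immediate reporting.
2. Reserve lactic acidosis for elevated lactate with bicarbonate below 22 mEq/L, the protocol's own exclusion threshold, or a clinical diagnosis where no bicarbonate is available, as in outside admissions. Count such cases even if the patient is then withdrawn.
3. Add bicarbonate to the listed follow-up laboratory tests; the re-review of exclusion criteria already needs it.
4. For lactate, apply the automatic stop only to lactic acidosis so defined, and state that the harm sentence does not act on elevated lactate alone.
5. Add elevated lactate by arm to the two-monthly report, using the scheduled samples with baseline taken into account and hospital values listed separately. Require a written Medical Monitor recommendation each time (continue, change dose, pause or stop). Send each lactic acidosis case to the Medical Monitor at once.

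**Cost.** Protocol wording, one recorded laboratory value and extra lines in an existing report. The real downside is the loss of a sensitive automatic trigger. At 400 per arm the statistical stop on lactic acidosis needs 4 v 0 and will rarely act, so protection rests on individual withdrawal and mandatory Medical Monitor review. The remaining false-stop rate depends on the unknown frequency of the new event: about 0% at the Potential Risks rates, 14% if 4 cases per arm are expected.

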#### **Outcomes and Assessment of Efficacy:**

The primary outcome by intention to treat analysis will be maintenance of sinus rhythm by chart review, EKG, and Atrial Fibrillation Severity Score at 3 and 6 months after the initial attempt at rhythm control.

Secondary outcomes will include hospitalization related to arrhythmic events or medication side effects, number of antiarrhythmic medications, number of repeat ablations, BMI, Hemoglobin A1c, and number of thromboembolic events.

Pre-specified subgroup comparisons will include comparing patients randomized to metformin who have a 5% reduction in weight at 6 months to all control patients who achieve a 5% reduction in weight, and to all control patients.

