#### **Statistics:**

We expect a 30% recurrence of AF after patients undergo ablation. After ablation, we expect the recurrence of AF to be 30% less in the intervention group of patients on metformin than the control group.

Using an 80% power at a 95% confidence interval, the sample size of the control group (ablation only) and the intervention group (ablation plus metformin) will be 400 each for a two tailed study, accounting for up to a 3% attrition rate in each group. The total sample size of this study will be 800. It is estimated to take five years to accrue subjects.

Statistical methods employed to analyze outcomes will be a Pearson's  $X^2$  test for categorical variables. Analysis of Variance will be used for continuous variables. All tests are two-sided and P < .05 will be used to indicate a statistically significant difference.

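### The adverse-event stopping rule works in both directions, so a significant excess in the control group would end the trial; it needs reconciling with the harm rule in the same section

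*Combined protocol and SAP*

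**What the plan says.** Two statements in Assessment of Safety govern the same two-monthly review.

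- The first: "If a statistically significant harm is detected in the analysis of the safety data collected at 2 month intervals the protocol will be terminated". No arm is named. The section asks the Medical Monitor to protect enrolled subjects generally, and also charges the Monitor with "assessing such actions in light of an acceptable risk/benefit profile for metformin".
- The second, at the end of the section: "Adverse events will be reviewed every 2-months and a statistical analysis will be done". It then makes stopping mandatory if "any of these adverse events have occurred more frequently in either group in a statistically significant manner, the trial will be stopped".

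The section defines two adverse events. Lactic acidosis is "lactic acid >2.1 mmol/L as measured at either routine follow up or if measured during a hospitalization for any reason". A thromboembolic event is "any stroke, mesenteric ischemia, limb ischemia, or other event determined to be of an embolic etiology secondary to atrial fibrillation". Outcomes and Assessment of Efficacy lists among the secondary outcomes "number of repeat ablations, BMI, Hemoglobin A1c, and number of thromboembolic events", and Trial Objective and Purpose also names thromboembolic events as a secondary endpoint.

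Statistics sets the threshold: "All tests are two-sided and P < .05 will be used to indicate a statistically significant difference". It names Pearson's chi-square for categorical variables and gives no adjustment for interim looks. No efficacy interim analysis is planned.

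**The concern.** The second statement has no direction. According to Trial Design, controls receive standard care plus extra blood draws and EKGs, so an excess of events among them is not harm from the study drug. The rule nevertheless ends the trial.

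For thromboembolic events this matters more, because fewer events on metformin is a result that the trial sets out to measure as a secondary outcome. The more protective metformin is, the more likely the rule is to fire, possibly before the sinus-rhythm question is answered. The point concerns the direction of the rule. How often it is applied is a separate weakness that enlarges the effect.

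**Working it through.** **1. The plan's own figure.** The stopping rule has no stated operating characteristics. The only related figure is 400 per arm (Statistics: 30% recurrence, 30% less on metformin, read as 30% v 21%; 80% power; two-sided .05; 3% attrition).

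- n = [1.96√(2 × .255 × .745) + 0.8416√(.30 × .70 + .21 × .79)]² / .09² = (1.208 + 0.516)² / .0081 ≈ 367.
- With continuity correction: (367/4)[1 + √(1 + 4/(367 × .09))]² ≈ 389. With attrition: 389/.97 = 401.03, so 402. The stated 400 reproduces.
- Power without continuity correction is 82% at 388 per arm (400 × .97) and 54% at 200 per arm.

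**2. How little is needed to trigger the rule.** Z = (x₁/n − x₂/n) / √[p̄(1 − p̄)(2/n)]. At 200 per arm with 4 control events and none on metformin, p̄ = 4/400 = .01 and Z = .02/√(.01 × .99 × .01) = 2.01, which exceeds 1.96. The trial stops. Fisher's exact two-sided P for the same table is 2 × (200·199·198·197)/(400·399·398·397) ≈ .12.

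**3. Simulation inputs.** From the documents: 400 per arm, five years' accrual, two-monthly looks, Pearson P < .05. Follow-up is about 7.5 months per patient (six weeks before ablation plus six months after), so there are 60/2 = 30 looks during accrual and 34 to month 68. Assumed: uniform entry, event times uniform over the 7.5 months, thromboembolic events only, and the event risks below. The documents give neither a thromboembolic rate nor an expected effect on it.

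**4. Stops in which the control excess crosses first.** Ranges show the spread between repeated simulation runs. The last column sums the binomial probabilities of all tables with Z > 1.96 at 400 per arm.

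| Control v metformin risk | 34 looks, critical value 1.96 | Final look alone |
|---|---|---|
| 1% v 0.7% | 12% | 6% |
| 2% v 1.4% | 20% | 9% |
| 3% v 2.1% | 25-27% | 12% |
| 1% v 0.5% | 18-19% | 11% |
| 2% v 1% | 31-34% | 19% |
| 3% v 1.5% | 44-45% | 29% |
| 4% v 2% | 53-55% | 38% |

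**5. No true effect.** Control excess v metformin excess: 6.9% v 6.4% at 1% risk, 9.2% v 9.4% at 2%, 11.8% v 11.1% at 4%. With equal allocation the split must be about even. A rule that counts only a metformin excess at the same critical value therefore cuts the total at 2% from 18.6% (9.2 + 9.4) to about 9%. With both adverse events included and assumed rates of 1-10%, the totals are 28-41% for either direction and 14-23% for metformin excess only.

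**6. How much is due to repeated looks.** With a strict critical value of 2.9 at every look, the halving scenarios at 2-4% control risk fall to about 3-16%. In those scenarios at 1.96, the median number randomised at a control-excess stop is about 390-450.

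**7. Sensitivity to the test.** Fisher's exact test gives about 25% instead of 32% at 2% v 1%, and 8% instead of 18% at 1% v 0.5%.

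**The case against.** **The two statements may not conflict.** A reader might infer that one says stop only for metformin harm and the other says stop for anything. The documents do not go that far. The harm sentence names no arm, the Medical Monitor protects all enrolled subjects, and the second statement could be read as spelling out the first for both arms. The metformin risk/benefit wording points towards harm from metformin but does not settle it. What stands is an ambiguity that must be resolved.

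**A symmetric rule can be deliberate.** More strokes among controls is a safety matter for controls, and some trials do stop on it. That is fair. But such a stop is a stop for benefit and needs a stated boundary of its own. An unadjusted P < .05 on a sparse secondary event is not an adequate one.

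**The large figures come from the looks, not the direction.** Largely true. A reader might infer that the direction of the rule alone cuts power for the primary outcome to about 54%. It does not: stopping near 400 randomised is a product of 34 unadjusted looks, and a crossing at the final look comes after all 800 are enrolled and followed. The direction problem does survive a single look or a strict threshold, at a smaller size.

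**The event rates are guesses.** Also true. Halving the risk exceeds the only effect that the plan assumes, a 30% reduction in AF recurrence. At 0.5% v 0.25% the control-excess figure is only about 7%.

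**Conclusion.** The point holds in limited form. The text plainly makes a control-group excess a mandatory reason to stop, nothing elsewhere in the documents prevents it, and the overlap with a secondary outcome turns it into an unplanned stop for benefit. The harm sentence and the either-group sentence must be reconciled.

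The size is conditional. It is roughly 12-55% at the two-monthly looks for assumed control risks of 1-4% and reductions of 30-50%, and about 11-38% at the final look alone if metformin halves the risk. About half of the false stops under no effect are control-excess stops. A reader might infer from the upper figures that the trial is likely to end early for benefit. The documents cannot support that, because they give no thromboembolic rate and no expected effect.

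This is a should-fix: a cheap improvement to the monitoring rule, not a defect that invalidates the design.

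**What to change.** Amend Assessment of Safety so that both statements give one rule:

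- The automatic statistical stop applies only when a listed adverse event is significantly more frequent in the metformin group.
- Keep the two-sided P value of the Statistics section and add the direction as a second condition. This is equivalent to one-sided .025, so the critical value stays at 1.96. A one-sided .05 test (1.645) would loosen it and give back part of the gain.
- Report a significant control-group excess to the Medical Monitor for judgement, not as an automatic stop.
- Test thromboembolic benefit only in the final secondary analysis.

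The cost is a short protocol amendment with no change to sample size or data collection. The downside is that the trial no longer stops automatically when controls have more events; review by the Medical Monitor mitigates this. The change does not cure the unadjusted two-monthly testing, which needs its own correction and is best handled in the same amendment.
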